5.2 Recruitment Methods

Recruitment and retention procedure: Participants will be recruited using Internet social media websites (e.g., Facebook, craigslist) and select print/web portals that have been used successfully in several large studies. Advertisements will include a link to a study landing page with study information and blank entry forms for interested Veterans to enter contact information through VA Qualtrics on Fedramp, a secure, FISMA-compliant server used across government agencies with an authority to operate with the VA. We plan to enroll 36 participants in the protocol overall.

Participants will also be recruited through a data access request using data from the Corporate Data Warehouse. CDW contains financial, enrollment, demographic, diagnostic, treatment utilization, and other data across Veterans from 1979 to present. All study staff will be trained on accessing these records by [name]. Joint Longitudinal Viewer will be used to access medical records to prioritize recruitment of Veterans with an active SUD. This pre-screening will help reduce Veteran burden and unnecessary contact of Veterans who would not be eligible. Participants identified through this method will be screened using the same criteria as those recruited through social media websites and select print/web portals as described above. Potential participants will be mailed a personalized letter describing the study and provided with a toll-free number so that they can contact study staff if they are interested in participating as well as opt out of future contact. Potential participants may be recruited from other studies that are IRB approved following completion of those other studies or if deemed ineligible. Only study staff that are approved on those studies will recruit those participants. Providers may also refer participants to the study by emailing the research staff/team. Providers will be given the

approved recruitment letters that are provided to Veterans as well as the approved study landing page for information (content can be found on p. 54 of the approved advertising pdf).

Participants will receive compensation for their participation in the study. The compensation amount will be based on the schedule that follows:

Baseline Assessment	\$40
Post-treatment Assessment (w/in a week)	\$40
30-day Assessment (RCT only)	\$40

Therefore, the total compensation for completing all the study components would be \$80 for the Aim 1 one-arm trial and \$120 for the Aim 2 RCT. Payments will be made via direct deposit or check following each study procedure listed above. Participants who do not complete the entire study for any reason will receive compensation for the components that were completed per the above schedule of payments.

5.3 Informed Consent Procedures

There are two phases where informed consent could be obtained, when completing the screening for eligibility and when enrolling into the study following the screening and if eligibility criteria are met. Verbal consent to participate will be obtained for the screening and baseline appointment. Informed consent will be obtained by study personnel trained in human subjects' protections requirements and how to obtain and document informed consent.

5.4 Inclusion/Exclusion Criteria

Inclusion criteria: Participants will include men and women who:

- Are English-speaking
- Are 18 years of age or older
- Have access to a phone or computer
- Screen positive for active SUD of at least moderate severity based on the M.I.N.I.
- Screen positive for loneliness by scoring at least a T-score > 60 on the NIH Toolbox loneliness scale

We will use the Veteran Verification screening for Veterans recruited through social media advertising to help confirm Veteran status.

Exclusion: Veterans will be excluded on the basis of:

- Does not understand informed consent

Pregnant women will not be excluded from this study as no invasive medical procedures are being performed and there is no known risk to the mother or the fetus of the proposed interventions. The study will not include prisoners or institutionalized Veterans.

5.5 Study Evaluations

Loneliness: The 20-item Revised UCLA Loneliness Scale will be our primary outcome measure.⁴⁵ We will use the 5-item NIH Toolbox Loneliness Scale⁴⁶ as our loneliness screening measure. The NIH Toolbox Loneliness Scale is correlated highly ($r = .80$) with the Revised

UCLA Loneliness Scale.^{24,46} T-scores >60 indicate loneliness scores 1 standard deviation above the mean and will be used to assess eligibility.⁴⁷

Quality/Quantity of Social Interactions: The Duke Social Support Index (DSSI) assesses several domains of perceived social support, including social network size, social interaction, social satisfaction, and instrumental social support. Research supports the psychometric properties of the DSSI scales.⁴⁸⁻⁵⁰ Belongingness and Burdenomeness: The Interpersonal Needs Questionnaire (INQ-12) assesses thwarted belongingness (i.e., an unmet need to belong) and perceived burdensomeness (i.e., feeling like a burden to one's social support network). Research supports the scale's psychometric properties.⁵¹

Substance use: We will use the *Timeline Follow Back (TLFB)*⁵² to assess quantity and frequency of substance use, and percent days abstinent. For the baseline assessment, participants will complete the TLFB for the past 3-months. Facilitating participant recall, the TLFB will be completed at each assessment so there are shorter intervals. Consequences of substance use: The Inventory of Drug Use Consequences (InDUC-2) will be used to assess drug use consequences in the following domains: impulse control, social responsibility, physical, intrapersonal and interpersonal.⁵³ Consequences will be assessed for the last 3 months at baseline and the follow-up will be since the previous assessment.

Other key descriptive variables: Treatment utilization: We will assess participant past and current substance use and mental health treatment utilization at baseline and follow-up. We will also assess primary care and specialty medical care visits, both within and outside the VA. This will be done using a modified version of the Treatment Services Review (TSR).⁵⁴ Quality of life: The PROMIS Profile-29 will be used to assess the following: anxiety, depression, physical function, fatigue, sleep disturbance, ability to participate in social roles and activities, and pain interference.⁵⁵ Demographics and military background. At screening, we will assess participants' branch, deployment history, gender, age, educational background, employment, income, race, ethnicity, and marital and cohabitation status.

5.6 Schedule of Assessments

Schedule of Assessments – One Arm Trial			
Measures	Screening	Baseline	Post-Intervention
Informed Consent - Verbal	X		
Eligibility Review	X		
Demographics and Military Background		X	
Oral Fluid Samples		X	X
NIH Toolbox Loneliness Scale		X	X
Timeline Follow Back (TLFB)		X	X
Revised UCLA Loneliness Scale		X	X
Duke Social Support Index (DSSI)		X	X
Treatment Services Review (TSR)		X	X
PROMIS-29		X	X

Inventory of Drug Use Consequences - InDUC-2		X	X
Interpersonal Needs Questionnaire-12		X	X
Exit Interview			X

Schedule of Assessments - Randomized Clinical Trial				
Measures	Screening	Baseline	Post-Intervention	30-day Follow-up
Informed Consent - Verbal	X			
Eligibility Review	X			
Demographics and Military Background		X		
NIH Toolbox Loneliness Scale		X	X	X
Timeline Follow Back (TLFB)		X	X	X
Revised UCLA Loneliness Scale		X	X	X
Duke Social Support Index		X	X	X
Treatment Services Review (TSR)		X	X	X
PROMIS-29		X	X	X
Inventory of Drug Use Consequences (InDUC-2)		X	X	X
Interpersonal Needs Questionnaire-12		X	X	X
Exit Interview			X	

5.7 Data Analysis

We will track rate of recruitment per week, and the percentage of participants who complete the protocol, and each follow-up. Participant treatment adherence will be assessed by tracking attendance and homework completion. Session-by-session participant feedback will be used to examine potential reasons for drop-out and non-adherence to inform our small RCT. Therapist adherence scores for the individual sessions and the overall interventions will be assessed as the percentage of the content delivered. Interrater reliability for fidelity will be assessed using intra-class correlation coefficients. We will assess the internal consistency of competence using Cronbach's alpha. Treatment acceptability will be assessed with the modified AARS and exit interview for a richer understanding. For participants who choose to withdraw prior to completing the full protocol, attempts will be made to conduct exit interviews to assess treatment experiences and reasons for early withdrawal. Interviews will be audio-recorded and transcribed. Interview data will be analyzed using matrix analysis,⁵⁶⁻⁵⁸ a systematic technique for data reduction to thematically organize and analyze data using rows, columns, and cells of a table. This process is time efficient, aligns well with results of in-depth analyses, allows for accurate summarizing of data, and facilitates participant comparisons.⁵⁷ Matrices are also an effective way to share findings with interdisciplinary team members for discussion.⁵⁶ Following

the analyses, these matrices will be reviewed by the investigative team and expert panel in preparation for finalizing the intervention.

Consistent with descriptive analyses for pilot studies,⁵⁹ measure completion percentage and means and standard deviations for outcomes will be calculated at each assessment, including change scores and correlations across timepoints. We expect large standard errors due to small sample size. Distribution of scores will be examined to better evaluate how to analyze these data in future studies (e.g., dichotomizing/ categorizing vs. continuous). For continuous outcomes, Hedge's g will be calculated to identify a range of the pre-post effect size. Although such calculations are of limited benefit in determining the effect of the intervention, they can be helpful in identifying outcomes that are less sensitive to change. Correlations among baseline variables will be calculated to assess the potential for variables to be included as covariates in the larger trial. This may also be useful in identifying potential moderators and mediators for the future larger trial. For data quality and handling of missing data, descriptive statistics will help identify out of range values and outliers. We will examine bias in retention rates at both the univariate and multivariate level of analyses

Data storage, security, and confidentiality

Several procedures for protecting participant confidentiality will be implemented to reduce the risk of revealing participant identity. All informed consent forms will contain identifying information. In order to ensure confidentiality, each consent form will be labeled with a numeric identifier and will be stored in a double-locked file. These will be stored in separate double-locked files from other study materials. As noted in the Data Transport Memorandum, locked courier bags will be used to transport any sensitive study information (e.g., consents) outside VA.

The VA Informatics and Computing Infrastructure (VINCI) will be used for the storage of study data. VINCI is a major informatics initiative of the Department of Veterans Affairs (VA) that provides a secure, central analytic platform for performing research and supporting clinical operations activities. It is a partnership between the VA Office of Information Technology (OI&T) and the Veterans Health Administration Office of Research and Development (VHA ORD). VINCI includes a cluster of servers for securely hosting suites of databases integrated from select national VA data sources. VINCI servers for data, applications and virtual sessions are physically located at the VA Austin Information Technology Center (AITC), located in Austin, Texas. This secure enclave with 105 high-performance servers and 1.5 petabytes of high-speed data storage has multiple layers of security and disaster recovery to prevent data loss.

Study data will be kept in accordance with the Department of Veterans Affairs Record Control Schedule 10-1 (RCS 10-1). Storage and transfer of any Personally Identifiable Information (PII) or Protected Health Information (PHI) must be done in accordance with applicable VA and VHA policies and directives, state and federal regulations, and applicable statutes including the Health Insurance Portability and Accountability ACT (HIPAA). Unless explicitly requested and approved by data stewards, all sensitive patient data must remain on VINCI project servers and only aggregate data without PII / PHI may be transferred from VINCI.

Prior to being uploaded to VINCI for analysis, data will be stored on a secure VA server, which is password protected, and to which only IRB approved VA research personnel have access. Should any identifiable information need to be shared between research sites, research teams will utilize a secure, SharePoint site or electronic communication with PKI encryption. Any identifiable paper data will be stored in two separate locked file cabinets (one for informed consents and the other for paper questionnaire data) in the offices of the Center for Excellence for Suicide Prevention at the Canandaigua VAMC. After a participant completes the study, any identifiers will be removed from the paper questionnaire data immediately. Data analysis will occur in the VINCI framework.

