3.0 Objectives

The proposed study will provide critical feasibility and acceptability data on telehealth Cognitive-Behavioral Therapy for Loneliness for SUD (CBT-L/SUD) among Veterans with SUD who report loneliness. We will conduct a small single-arm trial ($n = 6$) for refinement of the intervention and study procedure. With the refined manual, Veterans with SUD reporting loneliness will be randomized to either CBT-L/SUD ($n = 15$) or CBT-SUD ($n = 15$). The specific aims are as follows:

Aim 1: Refine the CBT-L/SUD manual by conducting a one-arm trial among Veterans with SUD who report loneliness ($n = 6$). *We will deliver CBT-L/SUD as part of a small, single-arm trial. This trial will allow us to collect feasibility of treatment delivery, and treatment satisfaction and acceptability data to further refine the manual.*

Aim 2: Randomize participants to receive either CBT-L/SUD (n = 15) or CBT-SUD (n = 15) to assess feasibility and acceptability among Veterans with SUD who report loneliness.

We will assess: (1) treatment acceptability, (2) participant adherence to treatment, and (3) therapist fidelity. We will also assess outcome measure completion percentage, means and standard deviations, and level of correlation of repeated measurement of primary loneliness outcomes and secondary substance use outcomes.

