5.0 Study Procedures

5.1 Study Design

Study sample: We will initially recruit 6 veterans who screen positive for loneliness and screen positive for active substance use disorder to receive CBT-L. Once these 6 veterans have completed study procedures, we will recruit an additional 30 to be randomized to either CBT-L or CBT-L/SUD. This cohort will be randomized 1:1. The study will take place at the VA Center of Excellence for Suicide Prevention. Participants meeting study eligibility criteria will be enrolled in the one-arm trial to receive CBT-L.

Screening: The project coordinator will screen by phone following a script. Potential participants will provide verbal consent to complete the screening measures. Those individuals meeting eligibility who are interested in participating will be scheduled for a phone-based consent and baseline assessment appointment. Based on our past experience, we expect approximately 25% of all participants who complete the screening to be eligible to and interested in participating. Therefore, we expect to screen no more than 500 participants to reach our sample of 36.

Assessments and Intervention:

Participants will be enrolled following consent and will complete the baseline assessment. Participants will schedule a convenient time for their phone-based intervention sessions. Mid-treatment, post-treatment and 30-day post-treatment follow-up assessments will also be conducted by phone, depending on the phase of the study. Participants will be paid \$40 each assessment completed. The post-treatment assessment will also include an exit interview for participants to describe acceptability of the intervention. Total compensation will be up to \$80 for the pilot phase, and \$120 for the randomized phase.

CBT for Loneliness for Substance Use Disorders (CBT-L/SUD):

The study team recently created a CBT-L/SUD manual (see **Appendix**) starting from a translation of the Kall et al. CBT-L manual as the base.⁴² We then incorporated relevant content and worksheets from the VHA Brief CBT manual and worksheets from CBT-SUD into the CBT-L base.^{43,44} The study team met and discussed ways to integrate content into the CBT-L manual based on our conceptual model, existing literature on substance use and loneliness, and other pertinent content from the VHA Brief CBT manual (e.g., material from behavioral activation) and CBT-SUD manual (examples of negative thoughts; case history).

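### The modified AARS, the only quantitative acceptability measure named, is assigned to no assessment, and the provision for early withdrawers does not extend to it

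*Combined protocol and SAP*

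**What the plan says.** Section 3.0 sets out the Aim 2 outcomes: "We will assess: (1) treatment acceptability, (2) participant adherence to treatment, and (3) therapist fidelity". Acceptability also serves Aim 1, where the single-arm phase is to supply "treatment satisfaction and acceptability data to further refine the manual".

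Section 5.7 names two instruments: "Treatment acceptability will be assessed with the modified AARS and exit interview". It goes on to say that exit interviews will be attempted with participants who withdraw before finishing the protocol, and that interviews will be recorded, transcribed and summarised by matrix analysis. The AARS is not mentioned in that provision.

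Section 5.1 places the interview at a definite point: "The post-treatment assessment will also include an exit interview for participants to describe acceptability of the intervention". Both tables in 5.6, "Schedule of Assessments – One Arm Trial" and "Schedule of Assessments - Randomized Clinical Trial", carry an exit interview row marked at post-intervention. Neither has a row for the AARS. Section 5.5 does not describe the scale, and no item in the reference list is attached to it.

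**The concern.** A feasibility and acceptability pilot should be able to report its acceptability rating and say who supplied it. Here the only rating scale named for that outcome has no stated content, scoring or time point. The schedules do deal with acceptability, but only through the interview. Staff working from 5.6 have no instruction that tells them when to give the scale.

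The second part matters more for interpretation. People who leave therapy early are plausibly those who found it least acceptable. The plan foresees this and tries to interview them, but it does not ask for the rating at that contact. An interview explaining why someone left does not enter the AARS summary. The score could then come mainly from those who stayed and read too favourably, in arms of 15 where a few absent raters carry weight. A rating not asked for at the time may not be recoverable later.

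**Working it through.** The plan gives no figure for this point, so there is nothing to reproduce. The check sets the sections side by side.

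**Where the AARS appears**
- 3.0 Objectives: acceptability is listed first under Aim 2 and is an output of Aim 1; no instrument is named.
- 5.1 Study Design: acceptability at post-treatment is by exit interview only.
- 5.5 Study Evaluations: AARS absent.
- 5.6, both schedules: AARS absent; exit interview present at post-intervention.
- 5.7 Data Analysis: AARS named once, with no expansion, items, scoring, citation, timing or threshold. The sentence on early withdrawers covers the exit interview only.

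**Are the schedules meant to be complete?** The eight scales described in 5.5 (Revised UCLA, NIH Toolbox, DSSI, INQ-12, TLFB, InDUC-2, TSR, PROMIS-29) each have a row in both tables. Other planned items do not appear: the M.I.N.I. (5.4) has no row of its own, although it could fall under eligibility review; the NIH Toolbox scale is the screening measure but is not marked at screening; session-by-session feedback (5.7) has no row; and the mid-treatment assessment (5.1) has no column. Absence from the table therefore shows that collection is unspecified. It does not show that the scale will be left out.

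**Is there a contact at which it could be collected?** Payments in 5.1 and 5.2 are 2 × $40 = $80 in the single-arm phase and 3 × $40 = $120 in the randomised phase. These match the post-screening columns of the schedules. There is no separate paid contact for the AARS, and none is needed, because the post-treatment call already exists and is paid.

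**How much could missing raters matter?** This is an illustration. The dropout shares and the rating gap are assumptions, as the documents give neither.
- Inputs: 15 per arm (3.0); share without a rating 0%, 20% or 40%; non-raters 0.5 to 1.0 SD less favourable.
- Raters: 15 × (1 − share) = 15, 12 or 9.
- 95% half-width of the arm mean, in SD units = t(0.975, n − 1) / √n: 2.145/√15 = 0.55; 2.201/√12 = 0.64; 2.306/√9 = 0.77.
- Upward shift of the raters-only mean = (non-raters / 15) × gap. At 20% missing: 3/15 × 0.5 = 0.10 SD to 3/15 × 1.0 = 0.20 SD. At 40% missing: 6/15 × 0.5 = 0.20 SD to 6/15 × 1.0 = 0.40 SD.

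Even at the top of this range the shift is smaller than the sampling half-width (0.40 against 0.77 SD). It runs in one direction, however, and the confidence interval does not reflect it.

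**The case against.** The best reply is that this is a clerical gap in a descriptive pilot. Several parts of that reply stand.

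- A reader might infer that acceptability would go uncollected. It would not. The exit interview is scheduled in both phases for that purpose, has a stated analysis method, and is to be attempted with people who withdraw. Only the quantitative rating is unscheduled.
- A reader might infer that staff will not give the AARS because the tables omit it. The tables omit other items that must happen for the trial to run, so that does not follow.
- A reader might infer that the AARS will be answered only by completers. No section says when it is given, or that stopping therapy ends assessment. Section 5.7 counts protocol completion and each follow-up separately, and 5.2 pays non-completers for the components they finish. Someone who stops therapy may still take the post-treatment call.
- A worst case such as 12/12 = 100% favourable among raters against 12/15 = 80% among all assigned is arithmetically sound. It needs a dropout figure, an acceptable/unacceptable cut-off, and unanimous opposite views in the two groups. The plan supplies none of these; 5.7 plans means and standard deviations for outcomes.
- Section 5.7 also plans completion percentages and an examination of retention bias, so a shortfall in raters might be noticed.

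What the reply does not remove is the wording of the withdrawer provision. If the scale is meant to accompany the exit interview, the plan does not say so, and the text on early leavers asks only for the interview. Noticing afterwards that ratings are missing does not supply them.

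**Conclusion.** The point holds as a gap in specification with a plausible but unmeasured bias. The only quantitative measure named for the first-listed Aim 2 outcome is mentioned once, is undefined, and is assigned to no assessment. The rule for early withdrawers, as written, does not seek it from them. Any AARS summary therefore risks resting on those who stayed.

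The documents do not support saying that acceptability goes unmeasured, that the scale will certainly be omitted, or that a bias of a given size will occur. The shift of 0.10 to 0.40 SD rests on assumed non-rating of 20% to 40% and an assumed gap of 0.5 to 1.0 SD. With complete rating, or with no difference between raters and non-raters, it is zero. The case for acting is that the remedy is cheap and uses contacts the plan already has.

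**What to change.** 1. In 5.5, describe the modified AARS: full name, source, modification, items and scoring.
2. In 5.6, add a row for it at post-intervention in both schedules.
3. In 5.7, amend the withdrawer sentence so that the AARS is sought from everyone assigned to therapy, including at the exit contact already attempted with those who stop early.
4. Report the score with the number who rated out of the number assigned, by arm in the randomised phase and overall in the single-arm phase. Forcing all randomised participants into the denominator of the score itself would not suit a mean rating, and it could not apply to the six single-arm participants, who are not randomised.

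The cost is one description, one row in each table, one amended sentence, and a few extra minutes for participants who stop early. No new visit or payment is needed.
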